Additional intervention details

Participants can withdraw from the study if they choose by no longer responding to the survey links and may withdraw their data by contacting the UNC study team.

Multiple strategies have been implemented to maximize adherence to the trial protocol, including reaching out to participants via email with invitations and reminders each day, compensating them based on completion of the most important questionnaires.

There is no relevant concomitant care or interventions that are permitted or prohibited during the trial.

Outcomes

[figure not shown]
Primary

- LCC guit intentions at post test (day 21)
 - Average quit intention score measured by survey, Quit intention measured with 3 questions, the final
 quit intention score is a mean of the response to the 3 questions, on a scale of 1 to 4, where 1 indicates
 low intention to quit, and 4 indicates a high intention to quit.

Secondary

- Number of LCCs smoked in past day (each day)
 - Measured daily by survey
- Number of days smoked LCCs in past week (days 7, 14, and 21)
 - Measured weekly by survey
- Number of LCCs smoked in the past week (days 7, 14, and 21)
 - Measured weekly by survey
- Butting out LCCs (days 7, 14, and 21)
 - Measured weekly by survey
- Forgoing LCCs (days 7, 14, and 21)
 - Measured weekly by survey
- LCC quit attempts (days 7, 14, and 21)
 - Measured weekly by survey
- LCC quit intentions (days 7 and 14)

- Average quit intention score measured by survey, Quit intention measured with 3 questions, the final
 quit intention score is a mean of the response to the 3 questions, on a scale of 1 to 4, where 1 indicates
 low intention to quit, and 4 indicates a high intention to quit.
- Self-reported learning (day 21) (only conditions 1 and 2)
 - Measured by survey. Self-reported learning measured with one item on a 1 to 5 scale, where 1 indicates no learning, and 5 indicates a great deal of learning from the warnings in the study.

Sample Size

The sample size is based on quit intentions effect sizes from an RCT comparing graphic cigarette warnings to text only warnings (Brewer, 2016). Based on the effect size observed in that study, we would have 80% power at α =0.05 to detect a small change in differences between our groups (f=0.12).

Recruitment

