Data management will be conducted by the study team. Multiple processes have been implemented to ensure high data quality, including internal pilots to test the protocol and ensure that data collection instruments are working properly, and ongoing data monitoring will be conducted during data collection to ensure that any issues with data quality are caught early and fixed. A pilot of the protocol with actual participants will be conducted before the full study is launched and participants will be asked about their experience in the study at the end of the pilot to further ensure that the protocol is working as intended and ensure a high quality data collection.

Statistical Methods

We will analyze the data using intention-to-treat analyses. Our primary outcome is LCC quit intention at post-test. We will model LCC quit intentions with message condition (warnings with images, FDA proposed text-only warnings, and a no warning control) as the between-participant predictor.

Analysis methods will depend on the time point that the outcome was measured. Post-test measures will be analyzed differently than repeated measures from the daily survey and weekly surveys, as outlined below. All models will include a categorical indicator of day to control for the durable linear effect of time.

Analysis methods for post-test measures will use linear regression for continuous outcomes, including the primary outcome of quit intentions, and logistic regression for dichotomous outcomes. Imputation will be used so that all participants who were randomized to an intervention and completed at least one daily survey will be included in the analysis, consistent with intention to treat practices.

Secondary models will examine differences between groups for items measured multiple times in either daily or weekly surveys (ex., LCC behavior measures). For these models, we will use linear mixed modeling to account for the repeated measure design. Mixed models are appropriate to use and robust to missing data, so we will be able to include everyone who completed at least 1 daily questionnaire, consistent with intention to treat practices.

Secondary models will also be run for the primary outcome as well as secondary outcomes that include the number of daily surveys completed (This is a measure that is equivalent to the dose of the stimuli for the active condition and also applies to the control condition)

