Appendix B. List of Measures by Timeframe

Screener	Baseline	Daily (with messages)	Day 7 and 14 - Weekly Behavior Assessment	Post
Quality Participants	Consent Form Weekly Behavior Assessment Other tobacco use questions (14-28 items) • Cigarette use (2 items) • Motivation to quit smoking • Previous year LCC quit attempts • Nicotine Dependence (5 items) • Tripartite Risk (3 items) • Self-Efficacy • Response Efficacy • Open Mindedness • OTP Quit Intentions (0-7 items) • OTP Quit Attempts (0-7 items) Additional Demographics • Sexual orientation • Education • Household size • Income • Subjective Financial Status • Zip code	 Past day cigarillos Past day little cigars Past day cigarettes Past day e-cigarettes Warning/Study Stimuli Attention to stimuli 	LCC Behavior (5 – 9 items) Memory Cue Past week Cigarillos Days smoked Number smoked Butting out cigarillos Forgoing cigarillos Past week little cigars Days smoked Number smoked Butting out little cigars Days smoked Butting out little cigars Forgoing little cigars OTP (2-9 items) Tobacco products used in past week Past week large cigars Past week cigarettes Past week roigarettes Past week smokeless Past week oral nicotine Past week something else Past week NRT Past day items (4 items) Past day cigarillos Past day cigarettes Past day cigarettes Past day cigarettes Past day e-cigarettes	Weekly Behavior Assessment Other tobacco use questions (12-26 items) Motivation to quit smoking Nicotine Dependence (5 items) Tripartite Risk (3 items) Self-Efficacy Response Efficacy OTP Quit Intentions (0-7 items) OTP Quit Attempts (0-7 items) Stimuli Responses (11 items) Reactance (3 items) Recall Recognition (6 items) Quality Control Questions (8- 11 items) See stimuli (+follow up) Read text (+follow up) Understand questions (+follow up) Do study again Recommend study to friend Annoyed by study Anything to share

 Ability to complete longer surveys Ability to complete daily surveys 			 Past week blunts (2 items) LCC quit intentions (3 items) LCC Quit attempts Conversations (2 items) Other LCC warnings Cognitive elaboration (2 items) Perceptions of recent LCCs smoked (3 items) 	Difficulty with behavior recall

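### Nothing in the plan ensures that baseline, day-7 and day-14 quit-intention scores of people who stop inform the day-21 primary contrast

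*Combined protocol and SAP*

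**What the plan says.** **Outcomes.** The primary outcome is the day-21 quit-intention score, the mean of three items on a 1 to 4 scale. The same score appears among the secondary outcomes as "LCC quit intentions (days 7 and 14". The five other weekly outcomes (days smoked, number smoked, butting out, forgoing, quit attempts) are each listed for all three weekly time points.

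**Appendix B.** The weekly assessment contains "LCC quit intentions (3 items" and is also given at baseline and post-test. Four scores per person are therefore planned.

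**Statistical Methods.**
- "Our primary outcome is LCC quit intention at post-test", with condition "as the between-participant predictor". No baseline or interim score is named.
- "Analysis methods for post-test measures will use linear regression for continuous outcomes, including the primary outcome of quit intentions".
- "Post-test measures will be analyzed differently than repeated measures from the daily survey and weekly surveys".
- For post-test outcomes, imputation is meant to keep in the analysis everyone randomized who answered one or more daily surveys. The method and the variables are not given.
- Repeated items go to secondary linear mixed models, with the remark that "Mixed models are appropriate to use and robust to missing data".
- Every model is to carry a categorical day term.

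The protocol refers to a Statistical Analysis Plan for further detail. The text available holds no separate section of that kind.

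**The concern.** A person who answers on day 7 or 14 and then stops has left direct evidence about the missing day-21 score. The stated regression has no place for that evidence, and the imputation step may or may not use it. Two things are at stake.

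- **Precision.** Ignoring correlated earlier scores makes the contrast noisier than it need be.
- **Bias.** One arm sees image warnings, one sees text warnings and one sees nothing, so the reasons for stopping could differ by arm. If stopping depends on the last observed score, and does so differently by arm, an analysis that omits that score is biased. One that conditions on it is not.

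Attrition could be material. Enrolment may go up to 3,000 to obtain 750 usable completes, and withdrawing only requires not answering. Researchers are not blinded to condition, so a choice left open now could be made with allocation visible.

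**Working it through.** **1. The plan's own figure.** Sample Size gives 80% power at α = 0.05 for f = 0.12, without naming a test or an N. Taking N = 750 from Methods Overview, a three-group one-way ANOVA (noncentrality N·f²) has power 0.844; 80% needs N = 673. One pair of arms with 750/3 = 250 each and d = 2f = 0.24 gives 0.24·√(250/2) − 1.96 = 0.72, power 0.765. The 80% is not in dispute; d = 0.24 SD serves below as a reference effect.

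**2. Inputs the documents do not give.** Retention by week, SD, within-person correlations and any link between score and dropout are all assumed. The only anchor for retention is 750/3,000 = 25%, an extreme because 3,000 is a ceiling and part of the gap may be quality exclusions.

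**3. Precision, dropout unrelated to the score, both analyses adjusted for baseline.** Assume a baseline correlation of 0.60, weekly correlations of 0.70 and monotone dropout.
- Partial correlation between weeks given baseline: (0.70 − 0.36)/(1 − 0.36) = 0.531.
- Share of residual day-21 variance explained by day 7: 0.531² = 0.282. By days 7 and 14 together: 2 × 0.282/(1 + 0.531) = 0.369.
- Variance ratio, joint model to day-21 regression: (1 − 0.369) + (0.369 − 0.282)·p21/p14 + 0.282·p21/p7, where p is the share observed on that day.

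| Observed on day 7 / 14 / 21 | Closed form | Simulations, weekly correlations 0.70–0.75 |
|---|---|---|
| 85% / 70% / 57% | 0.631 + 0.071 + 0.189 = 0.89 | 0.84–0.89 |
| 60% / 40% / 25% | 0.631 + 0.054 + 0.118 = 0.80 | 0.82–0.85 |

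A ratio of 0.89 equals 1/0.89 = 1.12 times as many completers; 0.82 equals 1.22 times. At high retention the gain is small. With everyone observed on day 7, no baseline adjustment and correlation ρ, the ratio is 1 − ρ²(1 − retention), which at 90% retention is 0.975 (ρ = 0.5) to 0.936 (ρ = 0.8).

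**4. Bias, dropout dependent on the last score in one arm only.** The true day-21 difference is 0.24 SD.

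*People with higher scores stay* (log-odds 0.5 per SD; retention patterns and assumptions as in step 3, weekly correlations 0.70–0.75). The baseline-adjusted day-21 regression gives 0.30–0.31 (57% observed) and 0.35–0.36 (25%). The joint model gives 0.24 in both. With no true effect, the regression's two-sided error rate is 13–15% and 39–41%; the joint model's is 5%.

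*People with higher scores leave* (log-odds −0.5 per SD; everyone has day 7):

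| Retention | ρ | Imputed from arm and baseline | Imputed with day 7 added |
|---|---|---|---|
| 0.50 | 0.5 | 0.176 | 0.237 |
| 0.50 | 0.7 | 0.190 | 0.241 |
| 0.75 | 0.5 | 0.207 | 0.240 |
| 0.75 | 0.7 | 0.211 | 0.239 |

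The bias runs upward in the first case and downward in the second. Using the interim score removes it whether this is done by a joint model or by imputation. When dropout does not depend on the score, all methods give about 0.24.

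**5. Baseline adjustment matters in its own right.** At retention 0.50, ρ = 0.7 and dropout unrelated to the score, the completers' regression adjusted for baseline has standard error 0.063. An unadjusted comparison after imputation with day 7 has 0.076. An imputation route therefore also needs baseline in the analysis model.

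**6. The day term.** In a regression of day-21 scores alone, day is constant and its coefficient cannot be estimated. In a joint model it can.

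**The case against.** The strongest reply is that the plan already handles missing post-test scores. Imputation keeps in everyone with one or more daily surveys, and if it draws on days 7 and 14 it is as valid under missing-at-random as a mixed model. That stands. A reader might infer that early answers do not inform the primary contrast at all; the documents do not support this, because the imputation variables are neither listed nor restricted, and further detail may sit in the Statistical Analysis Plan that the protocol mentions.

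Three other inferences also go too far.
- *That mixed models were chosen because of missing data and then withheld from the primary outcome.* The stated reason is the repeated-measures design; "Mixed models are appropriate to use and robust to missing data" is an added remark, and post-test outcomes have their own missing-data method.
- *That the secondary mixed model must exclude day 21.* Listing the secondary time points as days 7 and 14 may only avoid naming the primary one twice. It does not settle which rows enter the model.
- *That missingness is greatest on day 21.* No figure says so. Under the Compensation Plan a paid participant may miss day 7 or day 14 but not day 21. Gaps may therefore be non-monotone, whereas the simulations in steps 3 and 4 assume people who stop do not return.

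The 39–41% error rate needs 25% retention and one-arm score-dependent dropout together, so it illustrates an extreme.

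**Conclusion.** The point holds as a gap in specification. The same score is planned four times, the primary model names only condition, and nothing ensures that the first three scores inform the day-21 contrast for people who stop. If the imputation omits days 7 and 14, the cost is about 11% to 18% of the variance under the assumed retention of 57% to 25% (the closed form reaches 20% at the lower end), and less at higher retention. Bias arises only if dropout depends on the interim score differently by arm. In the scenarios tried it ranged from 0.06 SD too low (0.176 − 0.24) to 0.12 SD too high (0.36 − 0.24). If the imputation includes those scores, most of the gain is already obtained. It does not follow that the primary result will be biased, since no retention, correlation or dropout figure in the documents settles that.

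**What to change.** Prespecify one of two routes. The primary outcome stays day-21 quit intention in both.

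1. **Joint model (preferred).** Fit one linear mixed model of the scores on days 7, 14 and 21 with condition, categorical day, condition-by-day, baseline score and an unstructured within-person covariance. Report the day-21 condition contrasts as primary and the day-7 and day-14 contrasts as secondary. This also gives the required day term a meaning. State how people with a daily survey but none of the three scores are handled, since they supply no outcome row.
2. **Imputation.** Keep the day-21 regression, adjust it for the baseline score, and multiply impute from arm, baseline, day-7 and day-14 scores. Limit the day term to models that span several days.

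The cost is wording only: no new data, and for the joint model a few more covariance parameters. If the separate Statistical Analysis Plan already specifies route 2, a cross-reference in Statistical Methods is enough.

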Gaps exist in understanding which LCC warning characteristics (i.e., content, format, size) are most influential in reducing LCC use, and how additional LCC policies, such as removal of flavor descriptors on packaging, influence the impact of LCC warnings. Our project will provide new data to fill these evidence gaps.

Our research on LCC warnings has found that the health effects included in warnings are the most important aspect of warning the warning statement text, and including multiple warnings can lead to stronger warnings, (Jarman, 2021) that that images paired with our warning statements that depict the internal harm or both internal and external harm of smoking LCCs were more effective. (Clark, 2022) In a 2x2 experiment to assess whether warning type (warning statement + image vs. warning statement only) and warning size (30% vs. 50%) were associated with perceived message effectiveness (PME), we found that the warnings that included images were higher in terms of PME than the warnings that were text-only, and that warning size were similar in terms of PME. (Goldstein, 2023)

Given the lack of research on LCC product warnings, our overarching goal is assess whether LCC warnings developed by the study team are more effective than the currently implemented health warnings on LCC products. Given this goal, the choice of comparators are: 1) Newly developed warnings (the six most effective warnings developed by the study team), 2) FDA proposed text-only warnings or 3) No warnings (control condition) in which participants will not see warnings.

Objectives and Hypotheses

Objectives

The proposed study will fill critical gaps regarding which characteristics make LCC warning most effective and provide needed evidence on how LCC warnings influence LCC behavioral intentions. Our overarching goal is to develop effective LCC warnings that reduce cancer and other health risks.

Hypotheses

- Newly developed warnings with images will increase LCC quit intentions more than FDA proposed text-only warnings and more than the control condition in which participants do not see packs or LCC warnings
- The FDA proposed text-only warnings will increase LCC quit intentions more than the control condition
- The warning conditions combined will increase LCC quit intentions more than the control condition
- Newly developed warnings with images will increase self-reported learning more than FDA proposed text-only warnings

Trial Design

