The study is designed to be a parallel group trial, with participants evenly allocated to each study condition, using a superiority framework.

Methods: Participants, Interventions, and Outcomes

Methods Overview

We will conduct a 3-week web-based RCT of U.S. adults who currently use LCCs. In this study, LCC warnings on packs will be electronically presented to participants over time to determine if newly developed LCC warnings increase quit intentions compared to FDA proposed text-only warnings and a control condition (in which participants do not see LCC packs or warnings.) We will apply a daily diary methodology to present LCC warnings on packs to participants over time. Qualtrics will contact, screen, consent and administer the survey. To enroll participants, Qualtrics will screen participants using our inclusion criteria and measures and invite eligible participants to enroll in the study. To collect at least 750 quality completes we anticipate enrolling up to 3,000 people.

At the beginning of the baseline survey (day 0), participants will first consent to participate in the study and then complete a questionnaire about their tobacco use and behaviors (e.g., intentions and quit attempts) and other measures of interest. At the end of the baseline questionnaire, survey software will randomly assign participants to one of the 3 study conditions. The three study conditions are: 1) Newly developed warnings (the six most effective warnings developed by the study team), 2) FDA proposed text-only warnings or 3) No warnings (control condition) in which participants will not see warnings. Participants will be contacted via email each day (at approximately 6am) to invite them to complete the survey for that day of the study protocol.

For subsequent days (days 1-6, 8-13, 15-20) participants will be contacted and asked to complete a daily survey which will assess their previous day use of LCCs, as well as cigarettes and e-cigarettes. During these daily surveys, participants assigned to condition 1 or 2 (i.e., the warning conditions) will view an image of a little cigar and cigarillo package with a warning according to the participant's condition. Participants within each warning condition will view a total of 6 different warnings over the course of 6 days each week, this will be repeated 3 times during the study, resulting in a total of 18 exposures. Participants will be required to view the warning for at least 5 seconds before answering questions.

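### Do four quit-intention comparisons without a stated primary contrast, and one unattached 80% power figure, require a change to the plan?

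*Combined protocol and SAP*

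**What the plan says.** Three of the four listed hypotheses concern quit intentions, and together they contain four comparisons:

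- "Newly developed warnings with images will increase LCC quit intentions more than FDA proposed text-only warnings and more than the control condition" (two comparisons)
- "The FDA proposed text-only warnings will increase LCC quit intentions more than the control condition" (one comparison)
- a pooled claim, that the two warning arms taken together do better than no warnings (one comparison)

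The fourth hypothesis, "Newly developed warnings with images will increase self-reported learning more than FDA proposed text-only warnings", concerns a secondary outcome.

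Statistical Methods is clear about the outcome: "Our primary outcome is LCC quit intention at post-test". It fits one linear regression with a three-level condition factor. It names no lead contrast, omnibus step, testing order or adjustment, and it refers to a separate Statistical Analysis Plan for more detail. That SAP is not part of the text reviewed here.

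The Sample Size section takes its effect size from a trial of graphic against text-only cigarette warnings. It then gives a power of 80% with alpha set to 0.05, described as enough "to detect a small change in differences between our groups (f=0.12". The only target number is in Methods Overview: "To collect at least 750 quality completes we anticipate enrolling up to 3,000 people".

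**The concern.** Two things look wrong.

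First, four tests on the primary outcome with no rule leave open which result counts as success. If each were tested at 0.05, the overall false-positive risk would exceed 5%, and any one of four findings could later be put forward as the main one.

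Second, the power sentence names no test, sample size or sidedness. An overall f across three groups does not fix the power of any single pair. The Background gives the overarching goal as finding out whether the new warnings outperform those now in use, which is new against FDA. A reader could take 80% to be the chance of success on that question when it might be lower.

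**Working it through.** **Inputs.** f=0.12, alpha 0.05 and power 80% (Sample Size); at least 750 completes (Methods Overview); equal allocation (Trial Design). Assumptions: two-sided tests, 250 completes per arm and a common SD of 1.

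**The stated 80%.**

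- *Three-group omnibus F.* Noncentrality = N·f² = 750 × 0.0144 = 10.8 on 2 and 747 df, critical F = 3.008. Power is 84.4%. A total of 673 would give 80%. At 750, the f detectable with 80% power is 0.114.
- *Two-arm reading.* d = 2f = 0.24. Noncentrality = 0.24 × √(250/2) = 2.683 on 498 df. Power is 76.4%. 80% needs d=0.251 or 274 per arm. The detectable f is 0.126.

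Neither reading gives exactly 80%, but the stated f of 0.12 lies between 0.114 and 0.126. On the omnibus reading the plan exceeds its claim.

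**Pairwise power at a fixed omnibus f=0.12.** Put control at 0, FDA at q·g and new at g. Then f² = g²·2(1−q+q²)/9, so g = 0.12/√[2(1−q+q²)/9]. The protocol gives no value for q.

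| q (assumed) | g | New vs FDA | New vs control |
|---|---|---|---|
| 0 | 0.255 | 81% | 81% |
| 0.25 | 0.282 | 66% | 88% |
| 0.5 | 0.294 | 38% | 91% |
| 0.75 | 0.282 | 12% | 88% |

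The low figures arise because the new–FDA gap, (1−q)·g, is itself being reduced: at q=0.5 it is only 0.147. They show sensitivity to an assumed pattern of means and contradict nothing in the plan.

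**Multiplicity.** Four independent tests would give 1 − 0.95⁴ = 18.5%. These four are correlated, being contrasts of only three means. Simulation with no effects (2,000,000 runs) gives:

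- any of the four significant, two-sided: 12.8%
- the three pairwise contrasts only: 12.2%
- any of the four in the hypothesised direction: 6.9%, against 2.5% for one test
- any of the four, with a significant omnibus F required first: 5.0% (2.9% directional)

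**Cost of a rule, at 250 per arm.**

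| Rule | Contrast and pattern | Power without → with rule |
|---|---|---|
| Omnibus gate | New vs FDA, d=0.24, FDA equals control | 76% → 71% |
| Omnibus gate | New vs FDA, d=0.24, control midway between warnings | 76% → 65% |
| Omnibus gate | New vs control, even spacing, f=0.12 | 91% → 84% |
| Fixed order, new vs FDA first | New vs control, even spacing, f=0.12 | 91% → 37% |
| Fixed order, new vs FDA first | Combined vs control, even spacing, f=0.12 | 81% → 30% |
| Bonferroni over four | New vs FDA, d=0.24 | 76% → 57% |

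No rule is free, and the three take power from different contrasts.

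**The case for a change.** The strongest case for a change is that new against FDA is the main question, yet nothing marks it as primary. The hypotheses themselves place FDA above control and below new, which is the pattern in which an overall f says least about that contrast (38% if FDA is halfway). One sentence in the protocol would remove any freedom to choose the headline result afterwards, at no cost in participants.

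Part of this stands: the text is silent on these points, and the calculations are correct. Four things weaken it.

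- The effect size is drawn from a graphic against text-only comparison, the analogue of new against FDA. Read that way, power is 76% at the floor of 750, and the 38% and 12% figures do not apply.
- The floor may understate the information available. Everyone randomised with at least one daily survey is to be analysed with imputation. At d=0.24 with FDA equal to control, new against FDA has about 78% with 333 per arm and 25% missing day 21, and about 82% with 1,000 per arm and 75% missing. Both assume data missing completely at random, a baseline correlation of 0.5 and 20 imputations.
- The 12.8% depends on unadjusted testing, which the plan does not state. The hypotheses are directional, so 6.9% is the more relevant figure.
- Writing in a gate while quoting ungated pairwise power would create a new mismatch: d=0.25 has 80% ungated, but 75% gated if FDA equals control and 69% if control is midway.

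**Conclusion.** No change to the plan follows. The power sentence is terse but not shown to be wrong: at 750 completes, evenly split and tested two-sided, it corresponds to 84% on the omnibus reading and 76% on the two-arm reading, either side of the stated 80%. Naming the test and the number would make it easier to read, but would alter neither the sample size nor the analysis.

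On multiplicity, there is one primary outcome at one time point. The four contrasts are written down in advance with their directions, and all come from one three-level factor. A competent analyst will report all four together, with new against FDA read as the central one because the Background makes it the goal. A reader who wants an adjusted result can then obtain one. Unadjusted testing would carry a 12.8% two-sided or 6.9% directional risk of any false positive under no effects. Against that, a formal rule costs new against FDA up to 11 points (omnibus gate) or 19 points (Bonferroni) at d=0.24, and a fixed order cuts new against control by 54 points under even spacing at f=0.12. That is a trade-off for the sponsor, and the separate SAP may already settle it.

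This conclusion rests on the protocol text alone. It would be different if that SAP or a report promoted whichever contrast happened to be significant.
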